8.1 Inclusion Criteria

To be considered eligible to participate in this study, a subject must meet all the inclusion criteria listed below:

1. Male or female \geq 18 years of age
2. Women of childbearing potential (WOCBP) or men whose sexual partners are WOCBP; must be able and willing to use at least 1 highly effective method of contraception during the study and for 30 days after the last dose of study drug. A female subject is considered to be a WOCBP following menarche and until she is in a postmenopausal state for 12 months or otherwise permanently sterile (for which acceptable methods include hysterectomy, bilateral salpingectomy, and bilateral oophorectomy). Highly effective methods of contraception include intrauterine contraceptive device; intrauterine hormone-releasing system; combined hormonal or progestogen-only contraception associated with inhibition of ovulation (oral, intravaginal, or transdermal); bilateral tubal ligation or occlusion; vasectomy; condom in combination with contraceptive cream, jelly, or foam; or abstinence. Male subjects must agree to not donate sperm during the study period after drug is given until the 30-day follow-up.
3. American Society of Anesthesiologists Physical Status Score of 1 to 3
4. Scheduled for an elective BR as listed below via open or laparoscopic (straight, hand-assisted, robotically assisted) approach
 - a) Small BR
 - b) Large BR (partial colectomy)
 - c) Total colectomy with ileo-rectal anastomosis
 - d) Rectal resection (low anterior resection)
5. Based on investigator assessment, subject's hospital stays anticipated to be \geq 4 calendar days (i.e., at least 3 overnight stays). It is anticipated that the subject will not be discharged until they have achieved upper and lower GI recovery per the protocol definition.
6. Eastern Cooperative Oncology Group performance status of 0 or 1
7. Ability to understand the study procedures, have agreed to participate in the study program, and have voluntarily provided informed consent

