8.5.1 Close Observation and Clinical Management Plan

If early signs of possible DILI are detected in a subject, close observation should be initiated, and Sponsor should be notified within 24 hours (See protocol [Section 12.6.8](#)).

Clinical signs and symptoms of possible DILI or severe hepatotoxicity that may trigger close observation include, but are not limited to, the following:

- Persistent fatigue, weakness, nausea/vomiting, anorexia, pruritis, vague abdominal pain or right upper quadrant pain or tenderness, fever, rash, eosinophilia (eosinophils > 5%) in the absence of more likely causes
- Peripheral edema, ascites, encephalopathy, GI bleeding

- ALT > 3-fold ULN in subjects with normal baseline levels or 2-fold increases above baseline in subjects with abnormal levels prior to drug exposure

Close observation includes:

- Repeating liver enzyme and serum bilirubin tests 2 or 3 times weekly (the initial retest will occur within 48 hours). Frequency of retesting can decrease to once a week or less if abnormalities stabilize or the study drug has been discontinued and the subject is asymptomatic.
- Obtaining a more detailed history of symptoms and prior or concurrent diseases
- Obtaining a history of concomitant drug use (including nonprescription medications and herbal and dietary supplement preparations), alcohol use, recreational drug use, and special diets
- Ruling out acute viral hepatitis types A, B, C, D, and E; autoimmune or alcoholic hepatitis; NASH; hypoxic/ischemic hepatopathy; and biliary tract disease
- Obtaining a history of exposure to environmental chemical agents
- Obtaining additional tests to evaluate liver function, as appropriate (e.g., INR, direct bilirubin)
- Considering gastroenterology or hepatology consultations

Note that if additional testing is conducted, this information should be recorded in the eCRF.

Note: for any subject in whom a concern for hepatotoxicity or DILI develops (i.e., any subject that meets criteria for close observation), a narrative summary will be provided to the chairman of the DSMB by the Sponsor (via the CRO DSMB manager) for review by the board. The initial narrative summary will be provided within 24 to 48 hours of Sponsor notification of identifying a subject that meets the close observation criteria and updated versions provided as additional information becomes available and/or is requested by the DSMB chairman.

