- ^m Samples for routine clinical liver function tests will include alkaline phosphatase, aspartate transaminase, alanine transaminase, total and direct bilirubin, prothrombin time and INR. If these tests have been performed within 28 days before surgery, but before consent is obtained, the LFTs need not be repeated unless deemed appropriate by the investigator. On Day-1 LFT do not have to be repeated if done within 14 days of Surgery and the LFT were within normal limits. On Day 1, this should be taken before study drug administration to represent baseline values. Liver functions tests to include PT/INR and will be obtained during screening, pre-surgery, Randomization Day 1, Day 4, Day 7, and Day 10 (if remaining in the hospital), and the day of hospital discharge. Liver function tests are needed at the 30-day follow-up visit only if LFTs were elevated at discharge and trending down. If a subject remains in the hospital for an AE of elevated tests, then levels will be followed until resolution. A local laboratory should be used for screening and before pre-surgery Day -1. A central laboratory should be used after randomization on Day 1 and future visits.
- ⁿ Subjects will be randomized 1:1:1 (TU-100 15 g: TU-100 7.5 g: placebo) and stratified by surgical approach (open versus laparoscopic). Study drug will be administered TID (3 times per day [i.e., 6 hours ± 1 hour apart]).

- ^o GI assessments are to be performed twice daily, morning and afternoon with assessments separated by at least 6 hours.
- ^p Subjects will record the following items in their eDiaries on all postoperative in-hospital study days: first flatus (record in real time), first BM (record in real time), nausea occurrence and bothersomeness (24-hour reflection), vomiting/retching occurrence/number of episodes (24-hour reflection), abdominal bloating occurrence and bothersomeness (24-hour reflection).
- ^q Blinded review and assessment of hepatobiliary AEs by an independent CEAC will be performed on an ongoing basis during the conduct of the study.
- ^r PK samples will be drawn only at designated sites at the following times below, and at early termination (not needed at hospital discharge). If a subject is terminating early on a day scheduled for a blood draw, a second sample on the day of termination should be taken if possible. If a subject is terminating early on a day not scheduled for a blood draw, at least 1 sample should be obtained that day if possible.

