10.2.4 Follow-up Period

Follow-up contact (10 to 14 days after last dose of study drug)

All subjects will be contacted via telephone (or in-person if still in the hospital) within 10 to 14 days after the last dose of study medication for follow-up that will include:

- Record concomitant medications
- Monitor AEs
- Review of data for hepatobiliary AEs
- Monitor prespecified postoperative complications
- Determine whether hospital readmission occurred and reason for readmission

A certified letter will be sent to any subject not contacted after 3 attempts by telephone.

Follow-up visit (30 days + 15 days after hospital discharge)

All subjects are to return for a follow-up visit 30 days (+ 15 days). Procedures to be conducted at this visit include:

- Perform physical examination, including weight. Any clinically relevant physical abnormalities (with the exception of surgical scars) that were not present at screening should be recorded as AEs.
- Record vital signs (blood pressure, heart rate, respiratory rate, and temperature)
- Record concomitant medications
- Monitor AEs
- Monitor prespecified postoperative complications
- Determine whether hospital readmission occurred and reason for readmission
- If elevated at discharge and trending down, then liver tests will be completed at the 30-day follow-up visit. If a subject remains in the hospital for an AE of elevated tests, then levels will be followed until resolution.

If a patient does not return for a scheduled visit, all necessary measures should be taken to contact the patient and document the patient's outcome.

Reasonable efforts should be made to contact subjects who are lost to follow-up. A certified letter will be sent to any subject not contacted after 3 attempts by telephone. These efforts must be documented in the subject's file.

Exceptional measure for COVID-19

Depending on the COVID-19 situation (and/or to reduce burden of patient travel as needed), measures below may be considered for the 30-day follow-up visit.

- Window for the 30 day follow-up can be extended to +15 days after hospital discharge.
- If subject is unable to come to clinic for in-person visit, then performing LFT laboratory tests (if needed) at a local hospital, or regional independent laboratory located near the subject will be considered. Local laboratory results should be documented in subject's file.

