Blood taken at screening or pre-surgery on Day -1 will be analyzed at a local laboratory facility. Blood taken post-surgery on Day 1 (Postoperative Day 1, before study drug administration), and Day 2 through Day 10 will be analyzed at the central laboratory facility. All laboratory reports must be reviewed, signed, and dated by the investigator. A legible copy of all reports must be filed with both the subject's eCRF and medical record (source document) for that visit. Any laboratory test result considered by the investigator to be clinically significant should be considered an AE (clinically significant AEs include those that require an intervention). Clinically significant abnormal values occurring during the study will be followed up until repeat test results return to normal, stabilize, or are no longer clinically significant.

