12.6 Adverse Events

12.6.1 Adverse Events

An AE is any symptom, physical sign, syndrome, or disease that either emerges during the study or, if present at screening, worsens during the study, regardless of the suspected cause of the event. All medical and psychiatric conditions (except those related to the indication under study) present at screening will be documented on the medical history eCRF. Changes in these conditions and new symptoms, physical signs, syndromes, or diseases should be noted on the AE eCRF during the rest of the study. Clinically significant laboratory abnormalities should also be recorded as AEs.

Subjects will be instructed to report AEs at each study visit. All AEs are to be followed up until resolution or a stable clinical endpoint is reached. Each AE is to be documented on the eCRF with reference to date of onset, duration, frequency, severity, relationship to study drug, action taken with study drug, treatment of event, and outcome. Furthermore, each AE is to be classified as being serious or nonserious. Changes in AEs and resolution dates are to be documented on the eCRF.

For the purposes of this study, the period of observation for collection of AEs extends from the time the subject gives informed consent until the follow-up visit. Follow-up of the AE, even after the date of therapy discontinuation, is required if the AE persists until the event resolves or stabilizes at a level acceptable to the investigator.

When changes in the intensity of an AE occur more frequently than once a day, the maximum intensity for the event should be noted. If the intensity category changes over a number of days, then those changes should be recorded separately (with distinct onset dates).

The DSMB will be periodically reviewing safety data.

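### The 30-day liver test is required only for elevations already falling at discharge, so a mild elevation that first appears on drug can leave hospital with no required retest

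*Combined protocol and SAP*

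**What the plan says.** Protocol Section 10, Table 1 footnote m, lists the scheduled liver function tests (LFTs) as screening, pre-surgery, "Randomization Day 1, Day 4, Day 7, and Day 10 (if remaining in the hospital), and the day of hospital discharge". The Day 1 sample is taken before the first dose and serves as baseline. For the post-discharge visit the footnote says "Liver function tests are needed at the 30-day follow-up visit only if LFTs were elevated at discharge and trending down". Section 10.2.4 gives the same rule: "If elevated at discharge and trending down, then liver tests will be completed at the 30-day follow-up visit". In both places the next sentence covers only subjects kept in hospital for an adverse event of elevated tests. The contact at 10 to 14 days after the last dose is by telephone, unless the subject is still in hospital, and lists no LFT.

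Three event-driven rules run alongside this schedule:

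- **Close observation (8.5.1, reported under 12.6.8).** The one listed enzyme threshold is "ALT > 3-fold ULN in subjects with normal baseline levels or 2-fold increases above baseline in subjects with abnormal levels". Signs and symptoms also trigger it, and the list is described as not exhaustive. The first retest is within 48 hours.
- **Clinically significant values (12.5).** "Any laboratory test result considered by the investigator to be clinically significant should be considered an AE"; such values are followed until they normalise, stabilise or cease to be significant.
- **Adverse events (12.6.1).** "All AEs are to be followed up until resolution or a stable clinical endpoint is reached".

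**The concern.** A retest matters most when a liver value is still rising or has not moved. The scheduled rule selects the opposite group: subjects whose values are elevated but already improving. It says nothing about a subject sent home with a rising or flat elevation.

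The incidence and severity of hepatobiliary adverse events is a secondary objective (6.1.2). Section 5.4 gives the systematic evaluation of drug-induced liver injury (DILI) risk as the reason for close safety oversight. Eligibility excludes ALT, AST, ALP, and total or direct bilirubin above the upper limit of normal (ULN), apart from an allowance for raised indirect bilirubin (8.2, criterion 19). Most elevations at discharge are therefore new since screening. Under the current wording, the scheduled 30-day LFTs come only from subjects who were already recovering. A mild rise on drug, without symptoms and judged not clinically significant on the day of discharge, could go unchecked.

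**Working it through.** The plan gives no figure to reproduce here. The check is to list the scheduled samples by discharge day, apply the 30-day condition, and see what the other rules add.

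**1. Scheduled values after the first dose.** For discharge on Day *d*, the scheduled sample days are Day 1 (pre-dose), whichever of Days 4, 7 and 10 are no later than *d*, and Day *d* itself. This assumes one draw when the two coincide and no unscheduled tests.

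| Discharge day | Sample days | Values after first dose |
|---|---|---|
| 2 | 1, 2 | 1 |
| 3 | 1, 3 | 1 |
| 4 | 1, 4 | 1 |
| 5, 6 or 7 | 1, 4 and discharge (for 7: 1, 4, 7) | 2 |
| 8, 9 or 10 | 1, 4, 7 and discharge (for 10: 1, 4, 7, 10) | 3 |

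**2. Can an elevation first seen on drug meet the condition?** Take Day 1 as normal and the discharge value as elevated. Classify each value as normal, low-elevated or high-elevated, and call the trend downward if the last value is below the one before it.

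- Discharge Day 3 or 4: 2 possible patterns (discharge low or high); 0 qualify, since the only preceding value is normal.
- Discharge Day 5 or 7: 3 × 2 = 6 patterns; 1 qualifies (Day 4 high, discharge low).
- Discharge Day 8 or 10: 3 × 3 × 2 = 18 patterns; 3 qualify (any Day 4 value, Day 7 high, discharge low).

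These counts show whether the rule can apply. They are not probabilities. For discharge by Day 4, the rule cannot reach an elevation that began on drug. It can reach one already present on Day 1 before dosing, provided it has fallen and is still raised.

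**3. Is discharge by Day 4 in the planned population?** Inclusion criterion 5 anticipates a stay of at least 4 calendar days with 3 nights. Surgery is on Day -1 and there is no Day 0, so with admission on the day of surgery the shortest anticipated stay covers Day -1, Day 1, Day 2 and Day 3, with discharge on Day 3. Discharge is expected to follow gastrointestinal recovery, for which Section 14.2 assumes medians of 34 to 48 hours. Day 2 discharge would be 3 calendar days, shorter than anticipated.

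**4. What do the event-driven rules leave uncovered?** Close observation reaches ALT above 3 × ULN from a normal baseline, a doubling from an abnormal baseline, and symptomatic cases. Section 8.5.1 lists no AST, ALP or bilirubin threshold. Sections 12.5 and 12.6.1 apply once the investigator judges a value clinically significant or an adverse event is recorded. Unscheduled assessments are discretionary (10.2). No retest is required for a non-falling, symptom-free elevation that is judged not clinically significant and meets no listed trigger. Examples are ALT between 1 and 3 × ULN from a normal baseline, or an isolated AST, ALP or bilirubin rise.

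**5. Size.** The protocol does not give the share discharged elevated and not falling. Under assumed shares:

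- 1%: 402 × 0.01 = 4.0
- 5%: 402 × 0.05 = 20.1
- 10%: 402 × 0.10 = 40.2

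These are subjects without a scheduled 30-day LFT, before removing those retested under 8.5.1, 12.5 or 12.6.1. For the two TU-100 arms only (2 × 134 = 268), the range is 268 × 0.01 = 2.7 to 268 × 0.10 = 26.8.

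**The case against.** The strongest reply is that the uncovered group is what remains after several safeguards, and that leaving such values to clinical judgement is ordinary practice. The investigator must review and sign every laboratory report (12.5). Section 6.2.3 calls for close observation of confirmed early DILI signals without naming an ALT floor. Section 12.1 requires clinically noteworthy changes to be recorded as adverse events. Close-observation reporting runs to 30 days + 15 days after discharge (12.6.8), and the telephone contact and 30-day visit both monitor adverse events, so late symptoms would bring a subject back in. The adjudication committee's charter, which is not available here, may ask for more. Section 14.7.1 rests the DILI assessment on adjudicated events rather than on the 30-day LFTs. The wording can also be read as a pairing: improving subjects go home and are rechecked, while others stay in hospital.

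Much of this stands as a limit on size. The gap is narrow, its frequency is unknown, and no named analysis is shown to be biased. It does not close the gap. Each safeguard needs a trigger, a symptom or a judgement of significance, and none requires a retest for the group described. Follow-up under 12.5 or 12.6.1 may also end once a value is stable, so a flat elevation can be closed out. The pairing works only if every subject with a non-falling elevation is kept in hospital, and the protocol does not require that.

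**Conclusion.** The concern holds. As written, the scheduled 30-day LFT follows up improving subjects and omits those whose elevation is rising or flat. For discharge by Day 4, it cannot reach an elevation that first appeared on study drug. The conclusion is limited to required tests and to elevations that no event-driven rule catches.

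The Day 4 result assumes no unscheduled in-hospital tests, and the Day 3 minimum stay assumes admission on the day of surgery. The range of about 4 to 40 subjects rests on an assumed 1% to 10% of 402 and is an upper count for the gap within that assumption. The sponsor should correct this: the trial sets out to evaluate liver risk systematically, and the present condition selects the less informative subjects for retesting.

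**What to change.** In Table 1 footnote m and in Section 10.2.4, delete *and trending down*, so that any subject with LFTs above ULN at discharge has LFTs at the 30-day visit. Add a cross-reference to 8.5.1 and 12.5 for earlier retesting when values are rising.

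The deletion closes the gap. The cross-reference adds little for the uncovered group, which by definition meets neither section, so its first required retest would still be 30 to 45 days after discharge. An earlier check would need its own sentence, since the 10 to 14 day contact is normally by telephone.

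The cost is three words in two places, the cross-reference, and about 4 to 40 more blood draws under the same assumption. Subjects already attend the visit, and a local laboratory is already allowed for those who cannot travel.

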10.1 Informed Consent

Before performing any study-related procedures, the investigator (or designee) will obtain written informed consent from the subject.

In the event that rescreening occurs (allowed as long as the subject did not undergo surgery), the individual is required to sign a new ICF and must be assigned a new identification number.

10.2 Study Procedures

Assessments and their timing are to be performed as outlined in the Schedule of Assessments ([Table 1](#)). [Section 12.5](#) specifies laboratory assessment samples to be obtained. Assessments and procedures scheduled at a visit where study drug is administered should be performed before administration of treatment unless otherwise indicated in the Schedule of Assessments ([Table 1](#)).

Efficacy assessments are described in [Section 11](#) and include GI assessments, eDiary assessments, time to ready for discharge, time to writing of hospital discharge order, time to discontinuation of IV fluids (transitioning to oral liquids), blood loss, need for blood transfusion, NGT removal time, postoperative NGT insertion, time to transition to oral analgesics, and postoperative complications. Safety assessments are described in [Section 12](#) and include vital signs, physical examinations, ECGs, laboratory assessments (hematology, chemistry and LFTs) and AEs including hepatobiliary AEs. PK sampling is described in [Section 13](#). The investigator may, at his/her discretion, arrange for a subject to have an unscheduled assessment, especially in the case of AEs that require follow-up or are considered by the investigator to be possibly related to the use of study drug. The unscheduled visit page in the eCRF must be completed. Study treatment discontinuation and study withdrawal/termination procedures are described in [Section 8.5](#). Subjects are to be contacted for follow-up visits by telephone (or visit in-person, if still in the hospital) 10 to 14 days after the last dose of study drug.

10.2.1 Standard Enhanced Recovery After Surgery Protocol

All subjects will be managed with an ERAS protocol as per hospital SOC. However, elements within ERAS protocols intended to manage GI recovery will be standardized and compliance measured to the extent possible within this trial. Although alvimopan (approved for the acceleration of upper and lower GI recovery after surgeries that include partial BR with primary anastomosis) is used in ERAS pathways to accelerate GI recovery, use of alvimopan in this trial is prohibited, as its use would confound results. Methylnaltrexone, naloxone (except for treatment of known or suspected opioid overdose), and prophylactic or routine use of metoclopramide are also prohibited. Other hospital-specific ERAS elements not listed below will be allowed ([Carmichael 2017](#), [Lassen 2012](#), [Gustafsson 2012](#), [Kelliher 2015](#), [Melloul 2016](#), [Pecorelli 2016](#), [Pedziwiatr 2018](#), [Warner 2017](#)). ERAS measures intended to manage GI recovery that will be standardized per protocol include [Section 10.2.1.1](#), [Section 10.2.1.2](#), and [Section 10.2.1.3](#).

